## 7. Data analysis

Anonymised study data will be stored on a password protected university computer. No personal data will be stored as participants will only be identifiable by their own unique PIN. If a participant decides to withdraw from the study for any given reason all the participant's data will be deleted.

Participant data will be compiled onto a computer spreadsheet for statistical analysis. Simple descriptive statistics will be used to characterise the study population. Diagnostic test results from primary care will be compared by statistical analysis and evaluated at a significance level at  $p < 0.05$ . Quantitative data from the POC assay will be analysed alongside medical records and clinical outcome at primary care.

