### **1.1 Study Setting**

The ASPIRE study is an uncontrolled observational feasibility study, and a collaboration between the University of South Wales and Cwm Taf Morgannwg University Health Board (CTMUHB). The study is based at Ysbyty Cwm Rhondda (YCR) and Keir Hardie

Primary Care (KHPC) centres, where participant recruitment will take place. Study participants will be invited to provide capillary blood samples (via finger prick sampling) for testing. The principal investigators are [name] at YCR and [name] at KHPC. Upon clinical assessment, and after provision of consent, participants will undergo an ARI (acute respiratory infection) POC assay. This is a dual marker immunoassay designed to detect raised levels of C-reactive protein and MxA in capillary blood. The assay uses the sensitivity of CRP and specify of MxA to aid in the differentiation of ARI's in Primary Care.

The POC assay results will be compared to the participants' clinical outcomes and the physician directed treatment pathway via reviewing medical records and by contacting the patient from 14 days after their visit.

The study is funded by a KESS award.

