### 3.0 Study Aims and Objectives

A Primary care administered POC dual marker immunoassay utilising new technologies allowing on-site “in-house” diagnosis of ARI's may reduce unnecessary antibiotic prescribing by defining the bacterial or viral source of the infection. The POC assay could be used to guide GP's patient treatment and management decisions.

The primary objective of the study is to determine whether the POC assay is useful in aiding clinicians in the decision to prescribe antibiotics (Table 1).

Primary aims	Secondary aims

 
• Use a POC assay to distinguish between bacterial and viral infection in the Primary Care setting.
 
• To assess the feasibility of using POCT to support clinician decision making in prescribing antibiotics.
 
	
 
• Produce data to evaluate usefulness of the POC assay.
 
• Compare POC assay use to other POC assays used in Primary Care.
 

**Table 1:** Primary & Secondary Study aims.

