### 4.0 Study Participants

The study population will be recruited from self-referred patients attending YCR and KHPC centres with a self-suspected acute respiratory infection (ARI). The study aims to collect a minimum of 140 participants using a pragmatic sampling regime. The feasibility study will

provide the data required to design and conduct a more detailed and statistically powered trial.

The ASPIRE study will not replace clinical judgement or expertise. Patient management actions will be based on clinical judgement independent of the POC assay results. The physician will only have access to this data after the patient has finished their consultation.

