## **6. Data collection**

The POC test result will be performed in a separate room after the consultation is over and the patient's treatment decided upon. The GP will be blinded to the study and presented an information sheet and consent form prior to the patient's consultation to agree upon these terms.

The POC assay outcome and the participant characteristics at presentation will be recorded on CRF 1. All patient identifiable data will remain at Keir Hardie and Ysbyty Cwm Rhondda Primary Care Centres. The following information will be collected:

Demographics: Age, Sex, Weight, Height

Clinical Findings, Arterial O2 Saturation, resting heart Rate, CRB, resting Respiratory Rate and (office) Blood Pressure (where available).

The CRF 1 will also record any additional tests the GP may have requested as per the standard treatment procedure such as sputum or PCT tests. CRF1 will record the final diagnosis.

CRF1 will include a tick-box to state whether the participant has agreed to participate in a follow-up call after 14 days of their initial appointment. Each participant will be asked if they would be able to conduct a short telephone call with the research student to discuss the

outcomes of the treatment. If consented, the participant will confirm this on a tick box on CRF 1 and will be asked to provide a suitable contact mode and time to call back on the follow up form. Follow up data will be recorded on CRF 2.

Participant's medical records will be reviewed at the Primary care Practice to collect data concerning follow up treatment after 14 days to determine whether patients returned for medical treatment post appointment. Patient medical records will also be used to determine the clinical judgment of the initial assessment i.e. where they prescribed antibiotics or not. The clinical judgement and course of treatment followed will then be compared to the course of treatment that would have been suggested by the POC dual marker immunoassay result.

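### Section 7 judges test comparisons by p < 0.05 alone, although a feasibility study of paired results needs discordance with confidence intervals, which a significance verdict does not give

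*Protocol*

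**What the plan says.** Section 7 (Data analysis) makes three analysis statements. Descriptive statistics will characterise the study population. Next, "Diagnostic test results from primary care will be compared by statistical analysis and evaluated at a significance level at" p < 0.05. Finally, quantitative assay data will be looked at together with medical records and clinical outcome. The second is the only inferential criterion in the protocol.

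Section 1.1 describes the design: "The ASPIRE study is an uncontrolled observational feasibility study". Section 4.0 gives the size, "The study aims to collect a minimum of 140 participants using a pragmatic sampling regime", and the purpose, which is to "provide the data required to design and conduct a more detailed and statistically powered trial".

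The primary objective in Section 3.0 is to "determine whether the POC assay is useful in aiding clinicians in the decision to prescribe antibiotics". The comparison closest to it is in Section 6, where the clinician's judgement and the treatment given "will then be compared to the course of treatment that would have been suggested by the POC dual marker immunoassay result".

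Two other comparisons could be meant by diagnostic test results. Section 6 records "any additional tests the GP may have requested as per the standard treatment procedure such as sputum or PCT tests", and a secondary aim in Section 3.0 is to "Compare POC assay use to other POC assays used in Primary Care".

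**The concern.** The stated criterion does not fit the stated purpose. To design the later trial, one needs the share of patients in whom clinician and assay would decide differently, and in which direction. A p-value supplies neither share.

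On paired yes/no data, the McNemar test asks only whether one direction of disagreement outweighs the other. Frequent disagreement in equal directions gives a null result, which could be read as agreement. A Pearson test on the same table asks whether the two decisions are associated, and a significant association is compatible with much disagreement. The protocol names neither test; they are shown because either could be used under the rule as written.

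**Working it through.** **Inputs from the protocol.** Minimum size 140 (Section 4.0) and level 0.05 (Section 7). The size is described as pragmatic and has no stated derivation, so there is no figure to reproduce. The protocol gives no discordance rate. All rates below are assumptions, with total discordance from 10% to 40%.

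**Step 1: one verdict, different discordance.** Let b be the patients for whom only the clinician chooses antibiotics and c those for whom only the assay suggests them. Discordance is (b + c)/140. The exact McNemar p is twice the lower tail of Binomial(b + c, 0.5) at min(b, c), capped at 1. For b = 12, c = 2: 2 × (1 + 14 + 91)/2^14 = 212/16,384 = 0.013.

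| Both yes, clinician only, assay only, neither | Discordance | Exact McNemar p | Pearson p |
|---|---|---|---|
| 45, 7, 7, 81 | 14/140 = 10% | 1.0 | 1.4e-20 |
| 40, 28, 28, 44 | 56/140 = 40% | 1.0 | 0.018 |
| 40, 12, 2, 86 | 14/140 = 10% | 0.013 | 1.2e-20 |
| 40, 40, 16, 44 | 56/140 = 40% | 0.0018 | 0.0053 |

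The first two rows share a null McNemar verdict and the last two a significant one. Pearson is significant in all four. Within each pair, discordance differs fourfold.

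**Step 2: how often exact McNemar is significant at n = 140.** The number of discordant pairs m follows Binomial(140, p10 + p01). Given m, the clinician-only count follows Binomial(m, p10/(p10 + p01)). The probabilities of all outcomes with two-sided p < 0.05 are summed.

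| Total discordance | Split and probability of p < 0.05 |
|---|---|
| 10% | 7%/3%: 0.24; 8%/2%: 0.54; 9%/1%: 0.86 |
| 20% | 12%/8%: 0.13; 15%/5%: 0.71; 16%/4%: 0.88 |
| 40% | 22%/18%: 0.09; 25%/15%: 0.42; 28%/12%: 0.84; 30%/10%: 0.97 |
| 40%, balanced | 20%/20%: 0.04 |

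The result follows the imbalance of the split and not the amount of disagreement. Over the unbalanced splits it runs from 0.09 to 0.97.

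**Step 3: what estimation gives.** The Wilson 95% interval is [p + z²/(2n) ± z√(p(1−p)/n + z²/(4n²))]/(1 + z²/n), with z = 1.96 and n = 140. For p = 0.40: (0.4137 ± 0.0823)/1.0274 = 32.3% to 48.3%.

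| Discordance | Wilson 95% interval | Half-width, points |
|---|---|---|
| 14/140 = 10% | 6.1 to 16.1 | 5.0 |
| 28/140 = 20% | 14.2 to 27.4 | 6.6 |
| 42/140 = 30% | 23.0 to 38.0 | 7.5 |
| 56/140 = 40% | 32.3 to 48.3 | 8.0 |

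Direction is estimated in the same way. In the last table of Step 1, clinician only is 40/140 = 28.6% (21.7 to 36.5) and assay only is 16/140 = 11.4% (7.2 to 17.8).

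**Step 4: if the rule governs the assay against GP-requested tests.** Only patients who had such a test form pairs. Five discordances, all one way, give 2 × 0.5^5 = 0.0625, and six give 2 × 0.5^6 = 0.031, so at least six are needed for significance. The protocol does not say how many patients will have another test. With an assumed 20, 40 or 60 pairs, five discordances are 25.0% (11.2 to 46.9), 12.5% (5.5 to 26.1) or 8.3% (3.6 to 18.1). None would be significant.

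**The case against.** The strongest objection is that this is detail for a statistical analysis plan, which is not at hand. Section 7 is an outline; naming a 0.05 level does not rule out estimates and intervals alongside it. This stands for the unnamed test and the unstated hypothesis, which are not counted as faults here. It does not remove the point, because the protocol does state a criterion and that criterion does not fit the study's declared purpose.

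The second objection is about scope. The p < 0.05 sentence concerns diagnostic test results, while the Section 6 comparison concerns treatment decisions. A reader might infer that the protocol will judge its primary objective by p < 0.05. It does not expressly say so, and the objection stands to that extent.

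Third, a reader might infer that all the comparisons are paired. Pairing is clear for clinician against assay, and for GP-requested tests where they were done. It is not established for other POC assays, since the protocol does not say that a second such assay is run on the same patient.

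Fourth, a reader might infer that 140 patients give weak power. The documents do not support this. The protocol's rationale is unnecessary prescribing, so one-sided splits are at least as plausible as balanced ones, and several of those in Step 2 give 0.84 to 0.97. Nor is a missing power calculation an error in a feasibility study that leaves powering to a later trial.

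**Conclusion.** The point holds in a limited form. The only inferential criterion that the protocol sets cannot supply the quantity that the later trial needs. Under the assumed tables, the same verdict at 140 patients is compatible with 10% and with 40% discordance, whereas the interval for that share would be about ±5 to 8 points wide.

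That the same verdict can accompany different discordance does not depend on which assumed rates are right, because it follows from what the tests measure. The sizes shown do depend on them, and on 140 complete pairs. No general claim about power is made. Clinical care is decided independently of the assay, so participants' treatment is not affected. This is a cheap improvement of minor to moderate priority.

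**What to change.** In Section 7:

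- Make the main result the paired 2x2 table of the clinician's antibiotic decision (yes/no) against the assay-suggested decision (yes/no).
- Report discordance overall and in each direction (clinician only, assay only), each with a Wilson 95% interval.
- Where the assay is compared with another test on the same patient, report it in the same way and give the number of pairs.
- Label all p-values exploratory.
- Fix before analysis, from the study's own pathway, how an assay result is classed as suggesting antibiotics or not. No clinical rule is proposed here.

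The cost is a few sentences and one added definition, with no extra data or patients. The downside is that no significance claim can be made.

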## 8. Data management and quality control

All personal identifiable data will be treated as confidential. Each participant will be given a PIN upon providing consent which will be used across all their records and linked to their consent form. The study will comply with the requirements of the NHS Trust Data Protection and Confidentiality policy, which is based on the Data Protection Act 2018, the Caldicott Principles and Welsh Government guidance (GDPR). Identifiable personal data will be stored securely on an NHS computer with access controlled by the study PI's. Patient consent forms will be stored in a secured, locked cabinet at Ysbyty Cwm Rhondda and Keir Hardie Practices and will be destroyed within 6 months of the study closing. Anonymous research data will be stored on a spreadsheet, which can be accessed by other members of the research team within NHS and University of South Wales. Only the coded and anonymised data will be kept at the University of South Wales, according to USW policy (GDPR and Data Protection act 2018) for 5 years after completion of the study and then destroyed.

The Study research team will meet at the beginning and end of data collection of the study. Weekly review meetings between the research student and CI/DOS will be used to ensure the study follows the protocol.

## 9. Ethical considerations and Clinical governance

The study is hosted by CTMUHB and sponsored by the University of South Wales. The study will have received ethical approval from the Faculty of Life Sciences and Education Ethics committee, University of South Wales and a local NHS Research Ethics committee (LREC). Governance issues will be approved by Health Care Research Wales and managed by Cwm Taf Morgannwg Health Board via their Research and Development Department. Sensitive issues surrounding contacting patients with underlying health conditions will be met by appropriate caution under guidance of the clinical advisor. Any issues of distress arising from the study will be met by the appropriate services provided by the Medical practice.

## **10. Reporting and Dissemination**

All data generated from the study will positively contribute to improving antibiotic stewardship in the NHS. The study will be presented by [name] as partial fulfilment of his PhD thesis. The processed anonymised data will be published in clinical journals and reported at appropriate professional meetings. KESS may advertise the study as a case study. Further reports for internal use and to the manufacturers of the assay will be made if requested.

## **11. Risks and Safety Reporting**

### **11.1 Possible disadvantages and Risks to Patients by Taking Part**

No adverse risks or disadvantages to patients taking part in this study is expected. There is a small risk of sharps injury from the lancet used for the finger prick test. There may be some minor discomfort and a small risk of infection.

If the patient or their healthcare professional believes that their participation in the study is negatively affecting the management of their condition in any way, they will be withdrawn from the study.

To monitor any potential risks or adverse effects, patient data will be reviewed at monthly study meetings.

### **11.2 Definition of a Serious Adverse Event**

A serious adverse event (SAE) is any untoward medical occurrence that:

- results in death
- is life-threatening
- requires inpatient hospitalisation or prolongation of existing hospitalisation
- results in persistent or significant disability/incapacity

Other important medical events may also be considered serious if they jeopardise the participant or require an intervention to prevent one of the above consequences.

### **11.3 Reporting Procedures for Serious Adverse Events**

The investigators will ensure that this study is conducted in accordance with relevant regulations and with Good Clinical Practice.

All SAE's (serious adverse event) will be reported to the research study team. The study does not anticipate reporting any SAE's, if the chief investigator believes that a SAE occurring is

related to the study it will be deemed a related unexpected serious adverse event (RUSAE). All SAE's identified by the local Investigator (PI) likely to be related to the protocol and be unexpected will be reviewed by the study team. The CI, local PI or other qualified NHS staff member may declare an SAE a RUSAE. This may be downgraded in discussion with the research team but if no agreement can be made the event should be reported as a RUSAE. A RUSAE once reported can be downgraded later upon the receipt of new information. The CI will then inform the local Research Ethics Committee (LREC) assigned to the study. RUSAEs must be reported to the REC within 15 calendar days of the CI (or their research team) being informed of the event.

## 12.0 Study timeline

The study is intended to progress over a period of 10 months. A timeline below describes an outline of the intended work plan.

### 10 Month Project Timeline

Task	Month 1	Month 2	Month 3	Month 4	Month 5	Month 6	Month 7	Month 8	Month 9	Month 10	Month 11	+	Status:
Ethics Submission	Ethics submission												
Recruitment of Patients		Recruitment of patients											
Data Collection			Data Collection										
Data Analysis				Data Analysis									
Dissemination								Dissemination					

